9.4 Protocol Consent Processes and Documents

Each subject will receive an oral and written explanation of the purposes, procedures, and risks of this study. The original signed consent form will be placed in the subject's medical record and a copy will be given to the subject. A member of the protocol team will be available to answer questions about the study to be performed.

All medical information collected from study participants will be kept in a locked file at the Montefiore Medical Center or The Heart, Lung, Blood, and Vascular Medicine Institute of University of Pittsburgh. Unique patient identifiers will be used to label all data. Strict standards of confidentiality will be upheld at all times.

The following is a list of Associate Investigators who are authorized to obtain informed consent:

[name], [name], [name], [name].research nurse [name]

10. Pharmaceutical Information

Supply: Sodium nitrite 2% cream and placebo will be compounded and provided by Pine Pharmaceuticals, New York.

Product description: The 2% cream consist of 0.02 g of sodium nitrite, respectively, in 1 g of aquaphor ointment and will be dispensed in 30 g tubes. The amount of sodium nitrite contained in 1 cm 2% cream is 5.50 mg.

Storage: Store at 2°C - 8°C in the refrigerator.

Stability: Stable for 36 months at 4°C.

Route of administration: Apply topically to the ulcerated area and cover with dressing two times a week.

Toxicities: Stinging and burning sensation, yellow pigmentation at the application site, and vasodilatation.

Placebo

Supply: Placebo cream will be provided by the Pine Pharmaceuticals, New York.

Product description: The placebo will be made from aquaphorointment.

Storage: Store at 2°C – 8°C in the refrigerator.

Stability: Stable for 36 months at 4°C.

Route of administration: Apply topically to the ulcerated area and cover with dressing two times a week.

11. Conflict of Interest

There is no real or apparent conflict of interest. However, in the interest of full disclosure, the patent application filed by the NIH Office of Technology: U.S. Provisional Patent Application No.

28

PI: [name] Version 5 62/077,622, filed on November 10, 2014, entitled "TOPICAL SODIUM NITRITE FORMULATION," and PCT Patent Application No. PCT/US2015/060015, filed on November 10, 2015, entitled "TOPICAL SODIUM NITRITE FORMULATION," has six inventors: [name], [name], [name], [name], [name], and [name], who were all NIH employees at the time of invention.

- Or. [name] is presently employed on the faculty of the University of Pittsburgh.
- oDr. [name] is presently employed on the faculty of the Albert Einstein College of Medicine.

12 Adverse Events Reporting

The Principal Investigator (or a physician member of the research team) and the study coordinator will assess each participant for any new or continuing adverse events. An adverse event is defined as any untoward medical occurrence in a subject of a clinical investigation that involves the administration of a pharmaceutical product. The event need not to have a causal relationship with the treatment. This includes any events that are not seen at baseline or, if present at baseline, have worsened in severity. These adverse events will only be collected during study treatment time. The severity and drug relationship will be determined, and any management required will be recorded. The investigator will review the clinical laboratory test results in a timely fashion. Only those results qualifying as adverse events, as defined above, will be recorded as an adverse event.

Table 2. Expected Adverse Events Possibly Related to Study Drug						
Severe stinging and burning sensation, requiring an increase in narcotic use.						
Peripheral vasodilation with hypotension (BP below 85/50, or symptomatic						
dizziness, tachycardia, or hypoxia as per the judgment of the PI)						
Methemoglobinemia >7.5%						

Acute chest syndrome Angioedema Angioedema Aplastic crisis Aplastic crisis/anemia Aplastic crisis/anemia Appendicitis Bone Infarction Cardiomegaly Cerebrovascular accident Cholecystitis, hepatic sequestration Cranial nerve palsy Decreased kidney function Decreased lung function Pever Renal Insufficiency/albuminuria Headache Hematuria Hematuria Reticulocytosis (10%-20%) Hemiplegia Hemolysis Hepatosplenomegaly Hyperplastic bone marrow Hyposthenuria Increase Jaundice Metabolic acidosis	Table 3. Expected Adverse Events Re	elated to Sickle Cell Disease
Aplastic crisis Aplastic crisis/anemia Osteomyelitis Arthralgia Pain Appendicitis Pain, joint Bone Infarction Pain, severe abdominal Cardiomegaly Priapisim Cerebrovascular accident Pulmonary embolism Cholecystitis, hepatic sequestration Pulmonary hypertension (worsening) Cranial nerve palsy Pulmonary parenchymal infiltrates on x-ray Pecreased kidney function Pyleonephritis Decreased lung function Renal Failure Fever Renal Insufficiency/albuminuria Headache Renal papillary necrosis Hematuria Reticulocytosis (10%-20%) Hemiplegia Retinal disease Hemolysis Retinal hemorrhage Hepatosplenomegaly Skin ulcers Hyperplastic bone marrow Splenic sequestration Hyposthenuria Sepsis Hyperkalemia Upper respiratory infection Increase Jaundice Urinary tract infection	Acute chest syndrome	Leukocytosis
Aplastic crisis/anemia Arthralgia Pain Appendicitis Pain, joint Bone Infarction Pain, severe abdominal Cardiomegaly Priapisim Cerebrovascular accident Pulmonary embolism Cholecystitis, hepatic sequestration Pulmonary hypertension (worsening) Cranial nerve palsy Pulmonary parenchymal infiltrates on x-ray Pecreased kidney function Pyleonephritis Decreased lung function Renal Failure Fever Renal Insufficiency/albuminuria Headache Renal papillary necrosis Hematuria Reticulocytosis (10%-20%) Hemiplegia Retinal disease Hemolysis Retinal hemorrhage Hepatosplenomegaly Skin ulcers Hyperplastic bone marrow Splenic sequestration Hyposthenuria Upper respiratory infection Increase Jaundice Urinary tract infection	Angioedema	Meningitis
Arthralgia Pain Appendicitis Pain, joint Bone Infarction Pain, severe abdominal Cardiomegaly Priapisim Cerebrovascular accident Pulmonary embolism Cholecystitis, hepatic sequestration Pulmonary hypertension (worsening) Cranial nerve palsy Pulmonary parenchymal infiltrates on x-ray Decreased kidney function Pyleonephritis Decreased lung function Renal Failure Fever Renal Insufficiency/albuminuria Headache Renal papillary necrosis Hematuria Reticulocytosis (10%-20%) Hemiplegia Retinal disease Hemolysis Retinal hemorrhage Hepatosplenomegaly Skin ulcers Hyperplastic bone marrow Splenic sequestration Hyposthenuria Sepsis Hyperkalemia Upper respiratory infection Increase Jaundice Urinary tract infection	Aplastic crisis	Metabolic acidosis
Appendicitis Bone Infarction Cardiomegaly Cerebrovascular accident Cholecystitis, hepatic sequestration Cranial nerve palsy Decreased kidney function Pelmonary parenchymal infiltrates on x-ray Pyleonephritis Decreased lung function Renal Failure Fever Renal Insufficiency/albuminuria Headache Renal papillary necrosis Hematuria Reticulocytosis (10%-20%) Hemiplegia Retinal disease Hemolysis Retinal hemorrhage Hepatosplenomegaly Hyperplastic bone marrow Hyposthenuria Repair Sepsis Hyperkalemia Upper respiratory infection Urinary tract infection	Aplastic crisis/anemia	Osteomyelitis
Bone Infarction Pain, severe abdominal Priapisim Cerebrovascular accident Pulmonary embolism Cholecystitis, hepatic sequestration Pulmonary hypertension (worsening) Cranial nerve palsy Pulmonary parenchymal infiltrates on x-ray Decreased kidney function Pyleonephritis Decreased lung function Renal Failure Fever Renal Insufficiency/albuminuria Headache Renal papillary necrosis Hematuria Reticulocytosis (10%-20%) Hemiplegia Retinal disease Hemolysis Retinal hemorrhage Hepatosplenomegaly Skin ulcers Hyperplastic bone marrow Splenic sequestration Hyposthenuria Sepsis Hyperkalemia Upper respiratory infection Increase Jaundice Urinary tract infection	Arthralgia	Pain
Cardiomegaly Cerebrovascular accident Pulmonary embolism Cholecystitis, hepatic sequestration Pulmonary hypertension (worsening) Pulmonary parenchymal infiltrates on x-ray Pulmonary hypernession (worsening) Pulmonary embolism Pulmonary embolism Pulmonary embolism Pulmonary hypernession (worsening) Pulmonary embolism Pulmonary embolism Pulmonary embolism Pulmonary hypertension (worsening) Pulmonary embolism Pulmonary embolism Pulmonary hypertension (worsening) Pulmonary hyperension (worsening) Pulmonary hypernession (worsening) Pul	Appendicitis	
Cerebrovascular accident Cholecystitis, hepatic sequestration Cranial nerve palsy Decreased kidney function Pulmonary parenchymal infiltrates on x-ray Pereased lung function Pereased lung function Pereased lung function Renal Failure Renal Insufficiency/albuminuria Renal papillary necrosis Rematuria Reticulocytosis (10%-20%) Retinal disease Remolysis Retinal hemorrhage Repatosplenomegaly Skin ulcers Repatosplenomegaly Skin ulcers Splenic sequestration Ryposthenuria Sepsis Hyperkalemia Urper respiratory infection Urinary tract infection	Bone Infarction	Pain, severe abdominal
Cholecystitis, hepatic sequestration Cranial nerve palsy Decreased kidney function Decreased lung function Fever Renal Insufficiency/albuminuria Headache Hematuria Hemiplegia Hemolysis Hepatosplenomegaly Hyperplastic bone marrow Hyposthenuria Hyposthenuria Pulmonary hypertension (worsening) Renal Failure Renal Insufficiency/albuminuria Renal papillary necrosis Reticulocytosis (10%-20%) Retinal disease Hemolysis Retinal hemorrhage Skin ulcers Splenic sequestration Hyposthenuria Sepsis Hyperkalemia Upper respiratory infection Urinary tract infection		Priapisim
Cranial nerve palsy Decreased kidney function Pyleonephritis Decreased lung function Renal Failure Fever Renal Insufficiency/albuminuria Headache Renal papillary necrosis Hematuria Reticulocytosis (10%-20%) Hemiplegia Retinal disease Hemolysis Retinal hemorrhage Hepatosplenomegaly Hyperplastic bone marrow Splenic sequestration Hyposthenuria Hyposthenuria Upper respiratory infection Increase Jaundice Urinary tract infection	Cerebrovascular accident	Pulmonary embolism
Decreased kidney function Pyleonephritis Decreased lung function Renal Failure Fever Renal Insufficiency/albuminuria Headache Renal papillary necrosis Hematuria Reticulocytosis (10%-20%) Hemiplegia Retinal disease Hemolysis Retinal hemorrhage Hepatosplenomegaly Skin ulcers Hyperplastic bone marrow Splenic sequestration Hyposthenuria Sepsis Hyperkalemia Upper respiratory infection Increase Jaundice Urinary tract infection	Cholecystitis, hepatic sequestration	Pulmonary hypertension (worsening)
Decreased lung function Fever Renal Insufficiency/albuminuria Headache Hematuria Hemiplegia Hemolysis Hepatosplenomegaly Hyperplastic bone marrow Hyposthenuria Hyperkalemia Decrease Insufficiency/albuminuria Renal papillary necrosis Reticulocytosis (10%-20%) Retinal disease Retinal hemorrhage Skin ulcers Splenic sequestration Sepsis Hyperkalemia Upper respiratory infection Urinary tract infection	Cranial nerve palsy	Pulmonary parenchymal infiltrates on x-ray
Fever Renal Insufficiency/albuminuria Headache Renal papillary necrosis Hematuria Reticulocytosis (10%-20%) Hemiplegia Retinal disease Hemolysis Retinal hemorrhage Hepatosplenomegaly Skin ulcers Hyperplastic bone marrow Splenic sequestration Hyposthenuria Sepsis Hyperkalemia Upper respiratory infection Increase Jaundice Urinary tract infection	Decreased kidney function	Pyleonephritis
Headache Renal papillary necrosis Hematuria Reticulocytosis (10%-20%) Hemiplegia Retinal disease Hemolysis Retinal hemorrhage Hepatosplenomegaly Skin ulcers Hyperplastic bone marrow Splenic sequestration Hyposthenuria Sepsis Hyperkalemia Upper respiratory infection Increase Jaundice Urinary tract infection	Decreased lung function	Renal Failure
Hematuria Reticulocytosis (10%-20%) Hemiplegia Retinal disease Hemolysis Retinal hemorrhage Hepatosplenomegaly Skin ulcers Hyperplastic bone marrow Splenic sequestration Hyposthenuria Sepsis Hyperkalemia Upper respiratory infection Increase Jaundice Urinary tract infection	Fever	Renal Insufficiency/albuminuria
HemiplegiaRetinal diseaseHemolysisRetinal hemorrhageHepatosplenomegalySkin ulcersHyperplastic bone marrowSplenic sequestrationHyposthenuriaSepsisHyperkalemiaUpper respiratory infectionIncrease JaundiceUrinary tract infection	Headache	
Hemolysis Retinal hemorrhage Hepatosplenomegaly Skin ulcers Hyperplastic bone marrow Splenic sequestration Hyposthenuria Sepsis Hyperkalemia Upper respiratory infection Increase Jaundice Urinary tract infection	Hematuria	, ,
Hepatosplenomegaly Hyperplastic bone marrow Splenic sequestration Hyposthenuria Sepsis Hyperkalemia Upper respiratory infection Increase Jaundice Urinary tract infection	Hemiplegia	Retinal disease
Hyperplastic bone marrow Splenic sequestration Hyposthenuria Sepsis Hyperkalemia Upper respiratory infection Increase Jaundice Urinary tract infection	Hemolysis	Retinal hemorrhage
Hyposthenuria Sepsis Hyperkalemia Upper respiratory infection Increase Jaundice Urinary tract infection		Skin ulcers
Hyperkalemia Upper respiratory infection Increase Jaundice Urinary tract infection	Hyperplastic bone marrow	Splenic sequestration
Increase Jaundice Urinary tract infection		•
	Increase Jaundice	

29

PI: [name] Version 5

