- Apply 2 layer compression wrap to leg (depending on the condition of theulcer)
- Use of topical or systemic antimicrobials

All participants will be requested to complete the Brief Pain Inventory (BPI) prior to initiation of the therapeutic portion of the trial.

Baseline visit: The following tests will be performed:

- 1. Baseline labs, which include CBC, reticulocyte count, CRP, ESR, LDH, hepatic panel, basic metabolic panel, ferritin, Pro-B Natriuretic Peptide (BNP), urinalysis, urine microalbumin, uric acid, urine pregnancy test (female at reproductive age)
- 2. Research labs: Pax gene, and stored 5-10 cc blood samples
- 3. Saliva for DNA analysis
- 4. The surface area of ulcer(s) will be measured and photographed with defined lighting, distance, exposure and camera type
- 5. A pain assessment tool (VAS assessment)
- 6. Brief Pain Inventory (BPI), ASCQ-ME, PROMIS surveys, Beck Depression Inventory

Screening visit and baseline visits can be combined in one appointment.

After at least two weeks of "run in period", where the patient is treated with standard of care therapies only, the total ulcer surface will be measured and, if there isn't a reduction of>25%, the patient will be randomized to receive sodium nitrite cream or placebo.

A biopsy of the ulcer will be obtained in patients that consent during the run inperiod.

Week 1/Visit 3: First application of "study cream". After cleaning the wound, the wound will be measured by light photography and manually by wound nurse, a microbiome sample will be obtained, and the "study cream" will be applied to all the ulcerated surfaces. Vital signs will be obtained before application to establish baseline MAP and post-application at hours 1, 2, 3, 4, 5. If no significant decrease in MAP pressure from baseline is detected (clinically significant hypotension, or symptomatic dizziness, tachycardia, or hypoxia as per the judgment of the PI), the patient will be discharged and instructed to return for a second application two to three days later. Methemoglobin will be obtained one hour ± 30 min after creamapplication.

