Sodium nitrite cream in association with citric acid has been used as a topical agent for the therapy of chronic leg ulcers in non-SCD patients. In these human studies, no systemic adverse events were noted. This reflects the prompt production of NO when nitrite is mixed with citric acid. The phase I study of topical sodium nitrite cream without an acid that we just completed did not cause significant elevation of methemoglobin. An oral formulation of sodium nitrite did not cause elevation on metHb, but caused modest decreases in blood pressure.⁴⁹

Blood Drawing: Some patients may experience localized bruising at the site where blood is drawn. Routine blood drawing protocol will be followed to minimize this risk.

Skin Biopsy: There is a small risk of bleeding and infection at the site of biopsy. There is a small but real risk of increase in localized pain for a short period of time. Lastly, we do not know if patients that have a tendency to develop leg ulcers, may develop a chronic ulcer after a biopsy.

ASCQ-me, PROMIS, Beck Depression Inventory: There are no risks or discomforts from taking part in the ASCQ-me, PROMIS, and Beck Depression Inventory Surveys other than possibly getting tired from answering the questions.

PI: [name] Version 5 *Brief Pain Inventory*: There are no risks or discomforts associated to completing the Brief Pain Inventory other than possibly "test fatigue" -- getting tired of answering questions.

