12.3 Guidelines for Serious Adverse Events Reporting

Serious adverse events are defined by the FDA as any untoward medical occurrences that result in death, are life-threatening, require or prolong hospitalization, cause persistent or significant disability or incapacity, result in congenital anomalies or birth defects, or are other conditions which in the opinion of the investigator represents significant hazards.

Any and all serious adverse events relating to the acquisition of blood samples, and the application of the study cream, will be reported in writing to the chair of the IRB. The written report of the serious adverse event (e.g., death or life-threatening adverse event) will be sent within 5 days if the serious adverse event is unexpected and possibly, probably, or definitely related to participation in the study. In the event that an adverse event or deviation occurs that could present an immediate or urgent danger to subjects, the IRB chair will be contacted immediately.

All serious adverse events and unexpected non-serious adverse events relating to the acquisition of blood will be summarized and reported at the time of the continuing review.

> PI: [name] Version 5

Vaso-occlusive crisis occurs frequently and at unpredictable intervals in subjects with sickle cell disease, often requiring hospitalization. These events are expected and they will be summarized and reported at the time of the continuing review.

13. Data and Safety Monitoring Plan

The PI will assemble an independent Data Safety Monitoring Board, composed by 4 individuals appointed from within and outside the institution to ensure safe and effective conduct of the trial. The DSMB may recommend early termination of the study for considerations of safety and efficacy. A progress report will be forwarded to the DSMB at these times. The DSMB will meet with the Principal Investigator annually to perform the following activities:

- a. Assess participant safety, including:
 - i. All protocol deviations and adverse events
 - ii. All scientific or therapeutic developments that may have an impact on the safety of the participants or the ethics of the study.
 - iii. Benefit/risk ratio of procedures and participant burden
- b. Evaluate trial progress, including:
 - i. Quality, accuracy, and timeliness of collected data and statistical analysis
 - ii. Selection, recruitment, and retention of participants
 - iii. Confidentiality of trial data

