 - iv. Efficacy of the study intervention
- c. Performance of clinical research sites, including:
 - i. Performance of clinical research pharmacy and the core lab
 - ii. Adherence to protocol requirements
- d. Make recommendations to the IRB and investigators, including:
 - i. Continuation or conclusion of the trial
 - ii. Amendments to the study protocol and consent forms

Safety Monitoring:

Principal Investigator: Accrual and safety data will be monitored by the PI. The protocol will be continuously evaluated for any unusual or unpredicted complications with the sodium nitrite cream.

Accrual and safety data will be monitored and reviewed annually by the Institutional Review Board (IRB). Prior to implementation of this study, the protocol and the proposed informed consent and assent documents will be reviewed and approved by the properly constituted Institutional Review Board (IRB) operating according to the 45 CFR 46 Code of Federal regulations. This committee must approve all amendments to the protocol or informed consent, and conduct continuing annual review so long as the protocol is open to accrual, open forfollow up of subjects or open for data analysis and sharing.

Data Management. The PI will be responsible for overseeing entry of data into an in-house password protected electronic system (RedCap web application) and ensuring data accuracy, consistency and timeliness. The principal investigator, associate investigators, research nurses and/or a data manager will assist with the data management efforts. RedCap will be the main electronic system for data collection while paper CRFs will serve as a backup. Data will be entered into RedCap in real time whenever feasible. However,data can also be abstracted from Clinical Center progress notes as well as intake form and the other paper based case report forms. For data not entered in real time, source documents will be kept in the subject binder and entered at a later time. Date of entry will be automatically recorded. Data will be stored in locked cabinets and in a password protected database until it is no longer of scientific value.

32

[figure not shown]
PI: [name]

Loss or Destruction of Data: Should we become aware that a major breech in our plan to protect patient confidentiality and trial data has occurred, the IRB will be notified.

	Screening€	Baseline	Run-in				Double-B	linded Stu	dy Treatn	nent Phase	2			EOS
Visit Number	0	1	2	3-4	5-6	7-8	9-10	11-12	13-14	15-16	17-18	19-20	21-22	23

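### Adverse events are collected only during study treatment, so events after the run-in biopsy can go uncollected, and section 12.3 leaves IRB reporting of serious biopsy events unclear

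*Combined protocol and SAP*

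**What the plan says.** - **Collection window (section 12).** "These adverse events will only be collected during study treatment time". The definition just before this is broad: "This includes any events that are not seen at baseline or, if present at baseline, have worsened in severity". The investigator or a physician on the team, with the coordinator, "will assess each participant for any new or continuing adverse events".
- **Biopsy timing (section 5.3).** "A biopsy of the ulcer will be obtained in patients that consent during the run inperiod". Section 5.2 calls it optional and lists it among the entry studies. Section 5.7 describes a 3-4 mm punch at the ulcer edge. The visit schedule marks it once, at the run-in visit.
- **Biopsy risks (section 9.3).** The protocol lists bleeding, infection and a short-term increase in local pain, and adds: "we do not know if patients that have a tendency to develop leg ulcers, may develop a chronic ulcer after a biopsy".
- **Serious events (section 12.3).** The written-report sentence covers "Any and all serious adverse events relating to the acquisition of blood samples, and the application of the study cream". The continuing-review sentence names only the acquisition of blood. The biopsy appears in neither. The section also has a five-day clause for unexpected serious events at least possibly related to taking part in the study, and a clause for immediate contact with the IRB chair when an event could present urgent danger.
- **Subjects who do not start cream (section 5.2).** Those whose wounds shrink by more than 25% in the run-in stay on protocol, with monthly wound measurement for up to six months or until closure. No adverse-event collection is described for them.

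**The concern.** The protocol performs a research procedure on the edge of a chronic ulcer, in patients prone to ulcers, and says openly that one of its possible consequences is unknown. It performs that procedure in a period that its own collection rule leaves out. The gap comes from a stated restriction, not from missing detail: a site that follows section 12 exactly records no adverse event between the biopsy and the first cream application.

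What is at stake is protection of subjects and oversight. The DSMB is asked in section 13 to review all adverse events and the benefit and risk of procedures, but it can review only what has been collected. The IRB may or may not hear of a serious biopsy complication, depending on how section 12.3 is read.

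**Working it through.** No figure in the plan belongs to this point, so the check sets the sections side by side.

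**1. Order of events in the visit schedule.** Baseline is visit 1 (about week -2), the run-in with the biopsy is visit 2 (about week -1), and randomization and first cream are at visit 3 (week 1). Cream applications run over visits 3-22 (weeks 1-10). Visits 3-22 carry their own heading as the blinded treatment phase, and in the run-in subjects receive standard wound care only. The run-in is therefore not study treatment time. It lasts at least two weeks.

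**2. Biopsy events under the section 12 rule.**

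| Event | Collected as an adverse event? |
|---|---|
| Starts after the biopsy, resolves before visit 3 | No: it lies wholly before the window |
| Occurs in a biopsied subject excluded after the run-in | No: the subject has no study treatment time |
| Starts in the run-in, still present at visit 3 | Can be: it was not seen at baseline (visit 1), and continuing events are assessed |
| First appears during treatment | Can be |

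In the last two rows, section 12 asks for drug relationship and Table 4 in section 12.2 grades relationship to the study product. Nothing records relationship to the biopsy.

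**3. Run-in infection.** A footnote to the eligibility criteria lets a patient who does not qualify because of infection at enrolment or run-in start two weeks after it clears. A biopsy-site infection handled in this way would be noticed, but it would have resolved before the window opens. It falls in the first row.

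**4. Serious events under section 12.3.**
- Written report: limited to blood sampling and cream application.
- Five-day clause: it speaks of participation in general, but follows directly on the previous sentence and can be read as confined to that scope. It also requires the event to be unexpected. Bleeding, infection and pain are foreseen in section 9.3, and Table 3 lists skin ulcers, osteomyelitis, sepsis and pain as expected in sickle cell disease.
- Urgent-danger clause: not restricted by procedure, so it could apply.

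**5. Between-arm comparison.** Section 8.1.1 compares the number of adverse events by arm. The biopsy comes before randomization, so an event that resolves before visit 3 cannot depend on the assigned arm.

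**6. Size.** The number affected would be the biopsied subjects with an event resolving before visit 3, plus the biopsied subjects excluded after the run-in who have any event. The plan gives no biopsy uptake, run-in exclusion rate or complication rate. The 50 to be randomized are not the denominator either, because biopsied subjects excluded earlier come on top of them.

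**The case against.** The strongest reply is that the plan observes these patients closely and that several routes could pick up biopsy harm. All ulcers are measured and photographed after the run-in, with a pain assessment each time. Wounds are then measured weekly on treatment and monthly afterwards, and monthly in subjects excluded after the run-in. A chronic ulcer after a biopsy would probably show in those data. The five-day and urgent-danger clauses name no procedure. In the continuing-review sentence, the restriction to blood acquisition might be meant only for non-serious events. The biopsy is optional, estimating its risk is not a study objective, and no endpoint is affected.

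Much of this stands, and it rules out stronger readings that a reader might infer:

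- *That biopsy harm is neither recorded nor reported.* Events that persist into treatment or first appear then can be recorded, wound and pain data exist throughout, and at least one reporting clause could reach a serious event.
- *That a complication persisting into treatment is discounted as already present at baseline.* Baseline is visit 1, before the biopsy, so such an event counts as new.
- *That biopsy infection would pass unnoticed into the treated ulcer.* The eligibility footnote expects run-in infection to be found and to delay the start.
- *That patients are told the risk is unknown but that it will not be followed.* The statement is in protocol section 9.3. The consent pages are not available, so what they say cannot be judged.

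The reply does not remove the two uncollected groups. Wound size and pain scores are not adverse-event records: they carry no seriousness or attribution, and they would not show bleeding or a treated infection as such. That section 12.3 can be read in more than one way is itself the reporting problem.

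**Conclusion.** The concern holds in a limited form. As written, two groups of events are not collected as adverse events: biopsy events that resolve before visit 3, and all events in biopsied subjects excluded after the run-in. IRB reporting of serious biopsy events is unclear, not absent. This is a gap in subject protection and reporting that should be corrected. It does not threaten the safety comparison in section 8.1.1 or any efficacy endpoint.

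The conclusion assumes that study treatment time begins with the first cream at visit 3, as the schedule's headings indicate, and that the biopsy is done in the run-in, as section 5.3 and the schedule both state. No rate or count can be attached to it from the documents.

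**What to change.** - **Section 12:** start adverse-event collection at consent, or at minimum at the biopsy. State that it includes biopsied subjects who never start cream. Use the existing visits and, for excluded subjects, the monthly wound measurements already planned.
- **Section 8.1.1:** tabulate events before the first cream separately, so that the arm comparison stays as planned.
- **Sections 12 and 12.2:** record relationship to the biopsy as well as to the study drug.
- **Section 12.3:** add the biopsy to the procedures named in the written-report and continuing-review sentences, and say whether the five-day clause applies to all research procedures.

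The cost is protocol wording and a little more data collection, with no new visit or procedure.
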